1. INTRODUCTION

This is a Phase 2, multicenter, randomized, placebo controlled, dose escalation study to evaluate the safety of INCB054707 [REDACTED] over an 8-week treatment period in men and women aged 18 to 75 years with moderate to severe HS.

The study includes 3 cohorts, and approximately 36 participants will be enrolled. In each cohort, approximately 12 participants will be randomized in a 3:1 ratio to receive either INCB054707 (n = 9) or placebo (n = 3). The total duration of therapy for all enrolled participants is 8 weeks followed by a 30-day safety follow-up period. After all participants in each cohort have completed the Week 4 study visit and assessments, a SRC will review safety data.

The purpose of this SAP is to provide details of the statistical analyses that have been outlined in the Study INCB 54707-203 Protocol.

2. STUDY INFORMATION, OBJECTIVES, AND ENDPOINTS

2.1. Protocol and Case Report Form Version

[figure not shown]
This SAP is based on INCB 54707-203 Protocol Amendment 1 dated 09 AUG 2018 and CRFs approved 28 AUG 2018. Unless superseded by an amendment, this SAP will be effective for all subsequent Protocol amendments and CRF versions.

2.2. Objectives and Endpoints

[Table 1](#) presents the objectives and endpoints.

Table 1: Objectives and Endpoints

Objectives	Endpoints
Primary	
To determine the safety and tolerability of INCB054707.	
 • Frequency, duration, and severity of AEs, clinical laboratory test results, vital signs results, ECGs, and physical examination findings.
Secondary	
To determine the systemic exposure to INCB054707.	
 • Population PK parameters of INCB054707.
To determine the efficacy of INCB054707.	
 • Proportion of participants achieving a HiSCR at each visit. • Proportion of participants achieving an AN count of 0 to 2 at each visit. • Mean change from baseline in the HS Pain NRS scores, worst and average pain, at each visit. • Mean change from baseline to Week 8 in the modified Sartorius scale score. • Mean change from baseline in the number of draining fistulas count at each visit. • Proportion of participants at each category of Hurley Stage at baseline and Week 8. • Proportion of participants with change from baseline in Hurley Stage at Week 8. • Proportions of participants in each HS-PGIC category during the treatment period. • Actual measurements in HS-PGIC at each visit.
To assess the need for rescue lesional treatment.	
 • Proportion of participants requiring rescue lesional treatment. • Number of interventions with rescue lesional treatment.
To assess patient-reported quality-of-life burden.	
 • Proportion of participants at each scoring category of DLQI at each visit. • Mean change from baseline in DLQI total scores at each visit.

3. STUDY DESIGN

This is a Phase 2, multicenter, randomized, placebo controlled, dose escalation study to evaluate the safety of INCB054707 [REDACTED] over an 8-week treatment period in men and women aged 18 to 75 years with moderate to severe HS with a targeted enrollment of approximately 36 participants.

The study includes 3 cohorts, and approximately 36 participants will be enrolled. In each cohort, approximately 12 participants will be randomized to receive either INCB054707 (n = 9) or placebo (n = 3; randomization 3:1). The total duration of therapy for all enrolled participants is 8 weeks followed by a 30-day safety follow-up period. After all participants in each cohort have completed the Week 4 study visit and assessments, a SRC will review safety data.

3.1. Randomization

The study includes 3 cohorts, and approximately 36 participants will be enrolled. In each cohort, approximately 12 participants will be randomized in a 3:1 ratio to receive either INCB054707 (n = 9) or placebo (n = 3).

3.2. Control of Type I Error

All statistical analyses are exploratory in nature. No alpha control will be implemented. Unless otherwise specified, all confidence intervals provided will be at the 95% confidence level.

3.3. Sample Size Considerations

The study is a standard dose-escalation design, and the sample size depends on the occurrence of safety findings. Approximately 9 participants will be randomized in each dose level, which will provide > 85% chance of detecting at least 1 AE of interest (eg, platelets, hemoglobin, absolute neutrophil count, liver functions, and infections) if the underlying rate is 20%.

3.4. Schedule of Assessments

See Protocol Amendment 1 dated 09 AUG 2018 for a full description of all study procedures and assessment schedules for this study.

4. DATA HANDLING DEFINITIONS AND CONVENTIONS

4.1. Scheduled Study Evaluations

4.1.1. Day 1

Day 1 is the date that the first dose of study drug (INCB054707) or placebo is administered to the participants.

4.1.2. Study Day

If a visit/reporting date is on or after Day 1, then the study day at the visit/reporting date will be calculated as

$$\text{Day \#} = (\text{Visit/Reporting Date} - \text{Day 1 date} + 1).$$

If the visit/reporting date is before Day 1, then the study day at the visit/reporting date will be calculated as

$$\text{Day \#} = (\text{Visit/Reporting Date} - \text{Day 1 date}).$$

A study day of -1 indicates 1 day before Day 1.

4.1.3. Baseline Value

Baseline is the last nonmissing measurement obtained before the first administration of INCB054707 or placebo.

When scheduled assessments and unscheduled assessments occur on the same day and time of the assessment or time of first dose is not available, use the following convention to determine baseline:

- If both a scheduled and an unscheduled visit are available on the day of the first dose and the time is missing, use the scheduled assessment as baseline.
- If all scheduled assessments are missing on the day of the first dose and an unscheduled assessment is available, use the unscheduled assessment as baseline.

4.1.4. Last Available Value

The last available value is the last nonmissing measurement obtained after starting INCB054707 or placebo and within 30 days after the last dose of INCB054707 or placebo.

4.1.5. Handling of Missing and Incomplete Data

In general, values for missing data will not be imputed unless methods for handling missing data are specified in relevant sections.

4.2. Variable Definitions

4.2.1. Body Mass Index

Body mass index will be calculated as follows:

$$\text{BMI (kg/m}^2\text{)} = [\text{weight (kg)}] / [\text{height (m)}]^2$$

4.2.2. Prior and Concomitant Medication

Prior medication is defined as any nonstudy medication started before the first dose of INCB054707 or placebo.

Concomitant medication is defined as any nonstudy medication that is started accordingly:

- Before the date of first administration of INCB054707 and is ongoing throughout the study or ends on/after the date of first study drug administration.
- On/after the date of first administration of INCB054707 and is ongoing or ends during the course of study drug administration.

A prior medication could also be classified as "both prior and concomitant medication" if the end date is on or after first administration of INCB054707. In the listing, it will be indicated whether a medication is prior-only, concomitant-only, or both prior and concomitant.

The start/stop dates recorded in the eCRF by the investigator and his/her research staff will be used to identify when a concomitant medication was taken during the study. Any missing start date must be queried for resolution. Unresolved missing start dates will be handled as follows:

- If the date is completely missing, the medication will be considered both prior and concomitant.
- If only the day is missing, and the last day of the month is before the first dose date on Day 1, then the concomitant medication will be considered as starting before Day 1, and the incomplete date will be imputed as the last day of the month.
- If only the day is missing, and the first day of the month is after the first dose date on Day 1, then the concomitant medication will be considered as starting after Day 1, and the incomplete date will be imputed as the first day of the month.
- If only the day is missing, and the month is equal to the month of the first dose date on Day 1, then the incomplete date will be imputed as the first day of the month.
- If both the month and day are missing, and the last day of the year is before the first dose date on Day 1, then the concomitant medication will be considered as starting before Day 1, and the incomplete date will be imputed as if it is the last day of the year. Otherwise, the incomplete date will be imputed as if it is the first day of the year.

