6.7. Concomitant Medications and Procedures

All concomitant medications and treatments (including over-the-counter or prescription medicines, vitamins, vaccines, and/or herbal supplements) must be recorded in the eCRF. Any prior medication received up to 28 days before the first dose of study treatment and 30 days after the last dose of study treatment will be recorded in the eCRF. A detailed history of prior medications use related to HS in the year before screening will be also be collected, as well as response to each treatment and reason for discontinuation.

Any addition, deletion, or change in the dose of these medications will also be recorded. Concomitant treatments/procedures that are required to manage a participant's medical condition during the study will also be recorded in the eCRF. The medical monitor should be contacted if there are any questions regarding concomitant or prior therapy.

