8.1. General Considerations

Summary tables may be replaced with listings when appropriate. For instance, an AE frequency table may be replaced with a listing if it only contains a few unique preferred terms reported on relatively few participants.

Unless otherwise stated, table summaries will be limited to AEs occurring within 30 days of the last administration of study drug.

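### Read plainly, the SAP's concomitant-medication rule gives no category to a drug started on treatment and stopped after the last dose; the effect is confined to one descriptive table and one listing flag.

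*SAP*

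**What the plan says.** SAP 4.2.2 sorts medications by start and stop date.

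- Prior: "Prior medication is defined as any nonstudy medication started before the first dose of INCB054707 or placebo".
- Concomitant, started before dosing: "Before the date of first administration of INCB054707 and is ongoing throughout the study or ends on/after the date of first study drug administration". This bullet sets no upper limit on the stop date.
- Concomitant, started once dosing has begun: "On/after the date of first administration of INCB054707 and is ongoing or ends during the course of study drug administration".
- Labels: in the listing "it will be indicated whether a medication is prior-only, concomitant-only, or both prior and concomitant". There is no post-treatment label.

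The missing-date conventions in the same section deal with start dates only. SAP 6.6 then reports numbers and percentages of participants by drug term and class, in Table 1.4.3 for concomitant medications, and Listing 1.4.1 shows the individual records.

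Other windows in the plan run past the last dose. Protocol 6.7 collects "Any prior medication received up to 28 days before the first dose of study treatment and 30 days after the last dose of study treatment". SAP 8.1 says that "table summaries will be limited to AEs occurring within 30 days of the last administration of study drug". The last available value (SAP 4.1.4) and the laboratory shift tables (SAP 8.3.2) also extend to 30 days after treatment stops.

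**The concern.** The two concomitant bullets treat the stop date differently. For a drug started before Day 1, stopping during follow-up does no harm. For a drug started on or after Day 1, stopping during follow-up appears to remove it from the definition, even if it overlapped study drug for several days. Such a record cannot be prior either, so none of the three labels fits.

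The records at risk are those near the last dose, including treatment for an event that led the participant to stop study drug and treatment for events in follow-up. Protocol 9.3 sends treatment for an adverse event to forms such as the prior and concomitant medication page, and the SAP tabulates events to 30 days after the last dose. A late event could therefore appear in the adverse-event tables while its completed treatment has no place in the medication table. With about 9 active participants per dose level, one participant moves a percentage by 1/9 = 11.1 points in any row where he or she has no other qualifying use.

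**Working it through.** **Plan's own figure.** The plan gives no number on this point. Its only design calculation (SAP 3.3: 9 participants, 20% rate, more than 85% chance of at least one event) reproduces as 1 − 0.8^9 = 0.866. It does not depend on the medication rule.

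**Two readings of the second bullet.** Let S and E be the start and stop days of the medication, with Day 1 the first dose and T the day of the last dose.

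- Plain reading: *ongoing* means no stop date. For S ≥ 1 the drug is concomitant if there is no stop date or E ≤ T.
- Alternative reading: the closing phrase about study drug administration also modifies *ongoing*. For S ≥ 1 the drug is concomitant if S ≤ T.

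**Test records.** The last column applies the overlap rule set out under the fix.

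| Start to stop | Last dose | Plain | Alternative | Overlap rule |
|---|---|---|---|---|
| Day −10 to −2 | 56 | prior-only | prior-only | prior-only |
| Day −10 to 65 | 56 | both | both | both |
| Day 20 to 30 | 56 | concomitant-only | concomitant-only | concomitant-only |
| Day 53 to 60 | 56 | **none** | concomitant-only | concomitant-only |
| Day 53, no stop | 56 | concomitant-only | concomitant-only | concomitant-only |
| Day 20 to 30 | 20 | **none** | concomitant-only | concomitant-only |
| Day 22 to 32 | 20 | **none** | **none** | post-treatment |
| Day 60 to 67 | 56 | **none** | **none** | post-treatment |
| Day 60, no stop | 56 | concomitant-only | **none** | post-treatment |

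On the plain reading, the Day −10 to 65 record is kept and the Day 53 to 60 record is not. A drug first taken on Day 60 and never stopped counts as concomitant although it did not overlap dosing. On the alternative reading, both records that straddle the last dose are kept, and only starts after the last dose have no label.

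**Which reading fits better.** On the alternative reading the words *or ends* do no work, because a drug that starts and ends during dosing was necessarily ongoing during dosing. That favours the plain reading without excluding the other.

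**Illustrative size, plain reading only.** Assume a course of L days starts with equal chance on any of Days 1 to T. It ends on S + L − 1, which exceeds T for the last L − 1 start days, so the share is (L − 1)/T. With T = 56:

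- L = 3: 2/56 = 3.6%
- L = 7: 6/56 = 10.7%
- L = 14: 13/56 = 23.2%

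The only antibiotic course whose length the protocol gives (Protocol 6.7.1.1) lasts 3 days and is allowed after Week 4. With starts spread over Days 29 to 56, the share is 2/28 = 7.1%. The 7- and 14-day lengths and the even spread are assumptions. On the alternative reading every one of these shares is zero.

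**The case against.** The strongest reply is that the sentence is ambiguous, not wrong. If the closing phrase covers both verbs, a drug in use at the last dose is concomitant, and the set of concomitant drugs started on or after Day 1 already matches the overlap rule. Only a label for post-treatment starts is missing. This stands as a possible reading and limits the claim. It does not remove it, because completed courses begun after the last dose still have no listing category, and two programmers could reasonably produce different versions of Table 1.4.3.

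The reply is also right about consequences. A reader might infer that these medications are lost to the safety or efficacy assessment. The documents do not support that. Nothing says an unlabelled record is deleted. Analgesic use has its own diary (SAP 7.1.6) and Table 2.1.13; rescue treatment has Tables 2.1.8 and 2.1.9 and Listing 2.8. No visible efficacy or adverse-event rule uses the prior or concomitant flag.

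A reader might also take the course percentages as the error in the table, or recompute them for someone who stops early: at T = 14 the formula gives 2/14 = 14%, 6/14 = 43% and 13/14 = 93%. SAP 6.6 counts participants, so someone with another qualifying use of the same drug is still counted. No document gives a Day 14 stop, and the 3-day antibiotic course could not fall on treatment in such a participant. A loss concentrated among those who stop for tolerability is plausible on the plain reading, but it cannot be sized from the documents.

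Finally, the concomitant bullets refer to first administration of INCB054707 alone, which might suggest that placebo participants have no reference date. SAP 4.1.1 defines Day 1 as the first dose of study drug or placebo, and SAP 6.5 uses the same shorthand when it computes compliance for all participants. This is loose wording, not a gap.

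**Conclusion.** The point holds in a limited form and is minor. On the plain reading, a medication started on or after the first dose and stopped after the last dose is neither prior nor concomitant. On the alternative reading, the gap shrinks to medications started after the last dose. Drugs with no stop date are kept on the plain reading, and drugs started before Day 1 and still in use at the first dose are kept on both.

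The effect reaches the counts in Table 1.4.3 and the category flag in Listing 1.4.1. The number of participants affected cannot be derived from the documents. The range of 3.6% to 23.2% of courses rests on the plain reading, even starts over 56 days and assumed lengths of 3 to 14 days; it describes courses, not table entries. Sample size is unaffected.

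**What to change.** Replace the two concomitant bullets in SAP 4.2.2 with one overlap rule. A nonstudy medication is concomitant if it started on or before the last dose of INCB054707 or placebo and either ended on or after the first dose or is still ongoing. Keep the prior definition, and add a fourth listing label, post-treatment, for medications started after the last dose. Every record with known dates then has a category, whichever reading was intended, and naming both treatments removes the placebo shorthand.

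The cost is a short wording change in the SAP and one programming condition for Table 1.4.3 and Listing 1.4.1. No new data are needed, since Protocol 6.7 already collects medications to 30 days after the last dose. The change should be made before the medication table is programmed.

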8.1.6.2. Disease Characteristics and Treatment History

A disease-targeted medical and treatment history will be collected at screening. A detailed history of prior medications use related to HS in the year before screening will be also be collected, as well as response to each treatment and reason for discontinuation.

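### SAP 4.2.2 classes a drug with a completely missing start date as both prior and concomitant even when its recorded stop date precedes the first dose, against the section's own condition

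*SAP*

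**What the plan says.** SAP 4.2.2 (Prior and Concomitant Medication) first defines the classes and then gives rules for missing dates.

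- Prior: "Prior medication is defined as any nonstudy medication started before the first dose of INCB054707 or placebo".
- Concomitant, for a drug begun before the first dose: it must be "ongoing throughout the study or ends on/after the date of first study drug administration".
- Both: a prior drug may also be concomitant "if the end date is on or after first administration of INCB054707".
- Use of recorded dates: the eCRF start and stop dates "will be used to identify when a concomitant medication was taken during the study".
- Scope of the missing-date rules: "Any missing start date must be queried for resolution. Unresolved missing start dates will be handled as follows".
- First of those rules: "If the date is completely missing, the medication will be considered both prior and concomitant".

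The remaining rules impute a partial start date from the month or year. None of the rules mentions the stop date.

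SAP 4.1.5 states that in general "values for missing data will not be imputed unless methods for handling missing data are specified in relevant sections". Section 4.2.2 does specify a method, so its rule applies.

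SAP 6.6 summarises the number and percentage of participants with prior and concomitant medications. The planned outputs are Tables 1.4.1 (prior), 1.4.2 (prior for HS) and 1.4.3 (concomitant), with Listings 1.4.1 and 1.4.2.

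**The concern.** The definitions turn on two dates, and for a drug begun before dosing it is the stop date that decides whether it is also concomitant. The missing-start rule assigns the dual class from the absence of one date and ignores the other. Where the recorded stop date precedes the first dose, the missing start leaves no doubt about the class, yet the rule assigns a class that the definitions exclude.

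Such records are possible by design. Protocol 6.7 collects any medication received up to 28 days before the first dose, and Protocol 5.2 criterion 11 requires several drug classes to be stopped before baseline. Some drugs in the database will have ended before Day 1.

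At stake is the accuracy of one descriptive table and one listing. Table 1.4.3 could show a participant as taking, during the study, a drug that the recorded stop date shows had already ended. Some of these classes are prohibited on study (Protocol 6.7.2), so the entry could mislead a reader. There is also a reproducibility problem: a programmer who follows the rule literally and one who carries the end-date condition over from the definition would produce different tables.

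**Working it through.** The plan states no figure on this point, so the check sets the rule against the definitions. Times are in days relative to the first dose.

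**Step 1: what a pre-dose stop implies.** A drug cannot start after it stops, so start ≤ stop. If stop < first dose, then start < first dose for every possible start. The drug is prior by definition. It is neither ongoing nor ended on or after the first dose, so it is not concomitant. The definitions give prior only, whatever the start date.

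**Step 2: compare by stop date, start date completely missing.**

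| Recorded stop | Definitions, over all possible starts | SAP missing-start rule | With the fix |
|---|---|---|---|
| 90 days before | prior only | both | prior only |
| 28 days before | prior only | both | prior only |
| 1 day before | prior only | both | prior only |
| day of first dose | both, or concomitant only | both | both |
| 20 days after | both, or concomitant only | both | both |
| ongoing | both, or concomitant only | both | both |

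In the first three rows the rule contradicts the definitions. In the last three it is either right or a conservative default, and the fix leaves it alone.

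**Step 3: an example inside the collection window.** Take a topical anti-infective used on HS lesions, start unknown after query, stopped 3 weeks (21 days) before Day 1.

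- 21 > 14, so the 2-week washout of Protocol 5.2 criterion 11g is met.
- 21 < 28, so Protocol 6.7 requires the drug to be recorded.
- By Step 1 the definitions give prior only; the missing-start rule gives both.

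A compliant participant would be counted in Table 1.4.3 and flagged as both in Listing 1.4.1.

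**Step 4: what one record does to the table.** With the planned 9 active participants per cohort, one participant is 1/9 = 11.1 percentage points of a dose group. That is the granularity of the table, not an estimate of the error. It applies only if the participant has no other concomitant drug under the same term. The documents do not allow the number of affected records to be estimated.

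**Step 5: partial start dates.** Suppose only the start year 2018 is known, the stop is 15 JUN 2018 and the first dose is in 2019. The last rule imputes a start of 31 DEC 2018, which is after the stop. Both dates still precede the first dose, so the class is prior only, which is correct. The imputed interval is impossible, but nothing is misclassified.

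**The case against.** The best defence is that the section can be read as a whole. The missing-date rules sit under a sentence saying that recorded start and stop dates establish on-study use, they deal with missing start dates only, and nothing in them expressly sets aside a known stop date. A programmer could apply the end-date condition already given in the definition. That reading is possible, but the rule is unconditional: it names the resulting class and does not stop at placing the start before or after Day 1. The text should settle the matter.

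A second defence is that the dual class is a cautious default that avoids missing on-study use. This stands where the stop date is missing or falls on or after the first dose, or where the drug is ongoing. It does not stand where a known stop date rules out on-study use.

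Several stronger readings are tempting, and the documents do not support them:

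- *TNF inhibitors or antibiotics stopped many weeks before Day 1 would appear as concomitant.* Drugs last taken more than 28 days before the first dose fall outside the general collection window. They would be collected as HS treatment history (Protocol 6.7 and 8.1.6.2: "A detailed history of prior medications use related to HS in the year before screening will be also be collected"), which has its own Table 1.4.2 and Listing 1.4.2. Nothing shows that these records feed Table 1.4.3, and nothing excludes them.
- *The rule would create protocol violations.* SAP 6.3 reports deviations recorded on the eCRF, not deviations derived from this flag.
- *Efficacy or safety results would be confounded.* No endpoint analysis in SAP 7.2 or Section 8 is described as using the flag, and all efficacy analyses are exploratory without p-values (SAP Section 7).
- *The partial-date rules also misclassify.* Step 5 of the working shows that the example does not.

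**Conclusion.** The point holds as an internal contradiction in SAP 4.2.2. For a drug with a completely missing start date and a recorded stop before the first dose, the stated rule gives both where the section's definitions give prior only, and no other section repairs this.

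Its size is minor. The effect is limited to the concomitant medication summary (Table 1.4.3) and the class flag in Listing 1.4.1. The trigger is narrow: day, month and year of the start must all be missing after a mandatory query while the stop date is known. How often that will happen cannot be told from the documents.

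The conclusion assumes that the rule is programmed as written and that at least one such record falls among the medications feeding Table 1.4.3. It does not extend to any endpoint, deviation count or safety conclusion.

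**What to change.** In SAP 4.2.2, make the first missing-start rule depend on the stop date: when the start date is completely missing after query and the recorded stop date is before the first dose of study drug or placebo, class the medication as prior only; when the stop date is on or after the first dose, the drug is ongoing, or the stop date is missing, keep the dual class. As the table in the working shows, this changes only the pre-dose-stop rows.

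As a tidy-up, add that an imputed start date may not be later than the recorded stop date. This changes no classification and only prevents impossible intervals in the data.

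The cost is one or two SAP sentences and a matching line of programming. No new data, CRF change or protocol amendment is needed.
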